	
 4) Previous radical treatment to the prostate (radiotherapy or surgery) 5) PSA increase of at least 3 assays in the same laboratory over the last 12 months. 6) 1-5 pelvic lymph node metastases detected with 18FCH-PET. A relapse in the dressing prostatectomy is associated possible. 7) Upper limit of lymph node metastases: aortic bifurcation 8) Respect of dosimetry constraints to organs at risk 9) Treatment with hormone therapy may be started before inclusion, to a maximum of three months prior to Day 1 of radiotherapy. This hormone will necessarily be preceded by a free interval treatment of at least 6 months since the last injection, by adding the duration of action of this predictable injection (1, 3 or 6 months) 10) Patient affiliated to a social security scheme 11) Patient Information and written informed consent form signed
NON-INCLUSION CRITERIA	
 1) Bone or visceral metastatic relapse associated 2) Para-aortic nodal relapse (the upper limit is tolerated aortic bifurcation) 3) More than 5 lymph node metastases 4) Proof of metastases at initial diagnosis 5) Evidence of distant metastases in the pelvic lymph nodes or outside the prostate bed prior pelvic lymph nodes irradiation. Irradiation of the bed of the prostate is not an exclusion criterion, but the junction between prior irradiation bed prostatectomy and radiation field pelvic lymph nodes should be examined carefully 6) Castration resistance defined by clinical or biochemical progression despite a combined androgen blockade 7) Known contraindications to pelvic irradiation (eg, chronic inflammatory bowel disease, ...) 8) Known contraindications to hormone therapy, according to standard recommendations in force 9) Serious hypertension not controlled by appropriate treatment 10) Other concomitant cancer or history of cancer (within 5 years prior to study entry), except basal cell or squamous cell carcinomas of the skin. 11) Patient with a psychological, familial, sociological or geographical potentially hampering compliance with the study protocol and follow-up schedule 12) Patient already included in another interventional study involving the approval of a cpp during his screening for the study Oligopelvis 13) Private person of liberty or major trust

E) INVESTIGATIONAL TREATMENT DESCRIPTION

Experimental procedure

- **Radiation therapy**

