A simultaneous integrated boost will be applied to PTVs. It will be administered 5 days per week during 5 to 7 weeks.

The radiation therapy will start three months (+/- 15 days) after the first injection of IADT.

General recommendations

The use of intensity-modulated radiation therapy (IMRT) is mandatory.

Irradiation will be delivered to patients with an empty rectum. It is recommended that the patient empties his bladder and rectum one hour before the planning CT scan and before each radiotherapy treatment, and then drink at least 1/3 L of water after voiding. The one-hour delay will be adapted to the patient's continence.

If the prostate bed has been previously irradiated, it is recommended that the irradiation be delivered with the bladder empty in order to avoid re-irradiation of the bladder due to overlapping fields.

Daily verification of patient's organ positioning using IGRT is mandatory.

The use of a record and verify processing software is mandatory.

Preparation of treatment

A planning CT of the pelvic cavity that includes all of the pelvic lymph nodes will be performed in the supine position, with intravenous contrast agent to aid visualization of the pelvic vessels. Oral contrast agent will also be administered to assist in the determination of the small bowel volume. The minimum CT resolution will be at least 3 mm thick slices every 3 mm, but thinner slices may be necessary for very small volume lymphadenopathy. Merging the CT with pelvic MRI may help to visualize the vascular axes and pelvic lymph nodes.

Fusion with FCH-PET (or PSMA-PET): The FCH-PET (or PSMA-PET) images will be segmented using a threshold adapted to the size of the lymphadenopathy. These images will be used to locate the pathological lymph nodes, but the tumor volume (GTV) will be contoured on the planning CT.

Target Volumes

a) Metastatic lymph nodes

GTV1 to GTV5 will be delineated on the planning CT-scan with the aid of FCH or PSMA PET.

A margin of 3-5 mm around the GTVs will define the clinical target volumes (CTVs).

An additional margin of 3-5 mm around the CTVs will define the planned target volumes (PTVs). The intersection between PTVs and small intestine will be removed from the PTVs.

b) Whole pelvic lymph node irradiation

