Pelvic lymph nodes will be contoured according to the recommendations in the GETUG consensus statement (20). The pelvic lymph node CTV (PLN CTV) will include the common iliac, external iliac, internal iliac, pre-sacral (S1-S3) and obturator regions. The PLN CTV will be based on the pelvic vessels (arteries and veins) with an expansion of 7 mm, reduced where necessary at the bone, muscle, bowel and bladder boundaries. The upper limit is defined by the bifurcation of the abdominal aorta. If the prostate/prostate bed has been previously irradiated, the lower limit will be modified in accordance with the previous dosimetry in order to avoid overlap with regions which have received more than 20 Gy.

A margin of 5 mm around the PLN CTV will define the PTV. The intersection between PTVs and the small bowel will be removed from the PLN PTV

c) Prostate bed

Irradiation of the prostate bed will be considered if the prostate bed has not been irradiated.

The prostate bed CTV (PB CTV) will be defined according to the recommendations of the RTOG consensus (21).

Boundaries

Below the upper edge of the pubic symphysis, the prostate bed boundaries are:

- anteriorly: the posterior border of the pubic bone;
- posteriorly: the rectal wall;
- caudally: 8–12 mm below the vesicoureteral anastomosis;
- laterally: the levator ani and internal obturator muscle.

Above the upper edge of the pubic symphysis, its boundaries are:

- anteriorly: including 1–2 cm of the posterior wall of the bladder;
- posteriorly: the mesorectal fascia;
- cranially: the end of the vas deferens or 3–4 cm above the pubic symphysis;
- laterally: the sacro-recto-genito-pubic fascia.

A margin of 7mm will be added to the PB CTV to form the PB PTV.

d) PB relapse PTV

In case of prostate bed relapse, a PB relapse GTV will be defined based on PET-CT and MRI. A margin of 3-5 mm around the PB relapse GTV will define the clinical target volume (PB relapse CTV).

An additional margin of 3-5 mm around the PB relapse CTV will define the planned target volume (PB relapse PTV).

e) Organs at risk (OARs)

OARs will be contoured as recommended by the RTOG (22). No margin will be added (PRV) around organs at risk.

- Bladder: the outer contour of the bladder on all sections where it appears. The bladder volume is the volume between the outer contour and an inner contour that is defined 7mm from the outer contour.

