- DVH for intestine, bladder and rectal wall, PTV and CTV that meet dose constraints;
- a statement that patients will be treated with an approved daily image guidance technique.

All treatment plans will be sent via a web-based platform for central review and approval prior to beginning radiotherapy.

Quality control of IMRT: all IMRT plans will undergo quality assurance evaluation with ion chamber measurements or an equivalent method of dose verification to verify the absolute dose for each IMRT field, and film dosimetry to measure the relative dose for each IMRT field, as is standard clinical practice. An independent monitor unit calculation may be substituted for ion chamber dosimetry when available.

Management of previously irradiated patients

When the prostate/prostate bed has been irradiated previously, a cumulative dosimetric study will be performed to assess for radiotherapy volumes overlap, and the 20 Gy isodose will be drawn.

If any PTV1-5 has received more than 20 Gy during a previous course of irradiation, the patient should be excluded from the study.

If less than 20 Gy was delivered to PTV1-5, the lower limit of PLN PTV will be restricted to PTV1-5. No modification of the dose constraints will be applied.

Dose adjustment

No dose adjustments will be made.

- **Hormonotherapy**

Hormone therapy is recommended Eligard 45 mg acting for 6 months.

It will be ideally administered the day of start of radiation therapy or within 3 months before the first day of radiotherapy.

Nevertheless, free prescription is left to investigators.

When using other hormonal strategies (anti-androgen agonists, LHRH antagonists or LHRH), an administration for six months will be critical.

F) STATISTICAL CONSIDERATIONS

SAMPLE SIZE DETERMINATION

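### The 20 Gy prior-dose exclusion names only the nodal targets, so the prostate-bed relapse target (66 Gy) is the one prescribed target with no condition on earlier irradiation

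*Combined protocol and SAP*

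**What the plan says.** All references are to the combined protocol and SAP.

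- **Exclusion rule** (section E, Management of previously irradiated patients): "If any PTV1-5 has received more than 20 Gy during a previous course of irradiation, the patient should be excluded from the study".
- **What PTV1-5 are** (Target Volumes, item a, metastatic lymph nodes): "GTV1 to GTV5 will be delineated on the planning CT-scan with the aid of FCH or PSMA PET". The PTVs are built from these nodal volumes by adding margins.
- **Pelvic nodal volume** (item b): after earlier prostate or bed irradiation the lower limit is moved "in order to avoid overlap with regions which have received more than 20 Gy".
- **Prostate bed** (item c): "Irradiation of the prostate bed will be considered if the prostate bed has not been irradiated". The PB PTV dose line repeats that condition.
- **Bed relapse** (item d): "In case of prostate bed relapse, a PB relapse GTV will be defined based on PET-CT and MRI". The Dose prescription section gives this target 66 Gy in 30 fractions of 2.2 Gy, with no condition.
- **Eligibility**: inclusion criterion 6 adds "A relapse in the dressing prostatectomy is associated possible", which I read as allowing an associated relapse in the prostatectomy bed. Non-inclusion criterion 5 says that earlier bed irradiation does not exclude a patient. Inclusion criterion 8 requires "Respect of dosimetry constraints to organs at risk".

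**The concern.** Consider a man whose nodes lie outside an old bed field and who also has a relapse inside it. His nodal PTVs pass the 20 Gy test, and no criterion turns him away. The protocol then leaves two readings of how to treat the bed lesion.

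- If item d) applies, the lesion is prescribed 66 Gy whatever the bed received before. This is the target most likely to lie in an old bed field, and it is the one without a prior-dose limit.
- If item c) governs everything in the bed, the lesion gets no dose. He is then enrolled with known disease left untreated, in a study whose background describes radiotherapy directed at PET-detected lesions.

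Centres could resolve this differently, and the plan reviewers have no written criterion for this target. The only formal toxicity trigger looks at toxicity one month after radiotherapy in the first 20 patients. It is not built to pick up late injury in a rare patient.

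**Working it through.** **1. Dose lines.** Fractions times dose per fraction gives 30 × 2.2 = 66 Gy (PTV1-5 and PB relapse PTV), 30 × 1.8 = 54 Gy (PLN PTV) and 30 × 2.1 = 63 Gy (PB PTV). Each total matches its dose line.

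**2. Each target against its condition on earlier irradiation.**

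| Target | Dose | Condition on earlier irradiation | Where |
|---|---|---|---|
| PTV1-5 (nodes) | 66 Gy | Patient excluded above 20 Gy | Management of previously irradiated patients |
| PLN PTV | 54 Gy | Lower limit moved away from regions above 20 Gy; restricted to PTV1-5 | Item b); Management of previously irradiated patients |
| PB PTV | 63 Gy | Only if the bed was not irradiated before | Item c); Dose prescription |
| PB relapse PTV | 66 Gy | None | Item d); Dose prescription |

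Three of four targets have a condition; one does not.

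**3. The 20 Gy statements.** There are five: one in item b), one under Dose constraints and three under Management of previously irradiated patients (the isodose, the exclusion and the rule below 20 Gy). None names the PB relapse PTV. The one under Dose constraints speaks only of dose to the metastatic pelvic nodes.

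**4. What the limits imply.** These sums are mine, not the protocol's. They are nominal physical doses with no biological correction.

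- PTV1-5: 20 + 66 = 86 Gy.
- PLN PTV: 20 + 54 = 74 Gy.
- PB PTV: 0 + 63 = 63 Gy.
- PB relapse PTV: D + 66 Gy, where D is the earlier dose and has no stated limit. With the 20 Gy rule it would be held to 86 Gy, like the nodes.

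**5. Do the organ-at-risk limits stand in for a prior-dose limit?** The rectum limits are V50 < 50 %, V60 < 35 % and V65 < 25 %. The bladder limit is that no more than 50 % receives over 65 Gy. All are volume limits, with no maximum dose. Just under 25 % of the rectum could exceed 65 Gy by any amount and still pass. Under item c) the bed is bordered behind by the rectal wall and takes in 1–2 cm of posterior bladder wall, and no PRV margin is added. Letting the PTV shrink to the CTV reduces the volume treated, not the dose to the CTV.

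**6. Statistical design.** With 63 evaluable patients and at least 39 successes required, the exact binomial gives alpha 0.0385 at 50 % and power 0.936 at 70 %, against 3.85 % and 93.5 % in the plan. No input to this calculation depends on the target definitions.

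**The case against.** The strongest reply is that the text already points to the answer. Item c) speaks of the prostate bed, not of one named PTV, and a relapse in the bed is in the bed. The section on previously irradiated patients deals only with PTV1-5 and a shortened PLN PTV. It would be odd to pull a 54 Gy field away from the old one and then give 66 Gy inside it. For a bed already irradiated it is "recommended that the irradiation be delivered with the bladder empty in order to avoid re-irradiation of the bladder due to overlapping fields", which also suggests that re-treatment there was to be avoided.

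The safeguards are real. Inclusion criterion 8 makes the organ limits a condition of entry. The limits are left unmodified when PTV1-5 received less than 20 Gy, in the same section that requires a cumulative dosimetric study. Applying them to the summed dose is the natural reading, though it is not stated. Organ protection takes priority over coverage, and every plan needs central approval before treatment.

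Most of this stands: in-bed re-irradiation was probably not intended and is unlikely. It does not close the gap. Items c) and d) are separate targets, and the dose section attaches the no-earlier-irradiation condition to the PB PTV line only. The cumulative study has no threshold or action for the relapse target. If item c) does govern, the protocol still does not say that the known lesion will go undosed.

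A reader might also infer that the protocol requires 66 Gy in an irradiated bed, because it says that no dose adjustments will be made. That sentence sits under its own general heading and does not mention earlier irradiation, so it does not support that reading.

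**Conclusion.** The point holds as a gap in the wording: one of four prescribed targets has no condition on earlier irradiation, and the eligibility criteria do not keep out the patient to whom it matters. It is a minor to moderate patient-safety fix. The number affected is unknown, probably few and possibly none. Alpha, power and sample size are unchanged.

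Three stronger readings are not supported.

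- **A very high cumulative dose.** Assuming an earlier bed dose of 60–70 Gy, the sum would be 126–136 Gy. The documents give no earlier bed dose, so no such total can be attributed to the plan.
- **A biased efficacy claim.** An undosed lesion would tend to add failures, so it would not flatter the result.
- **A patient outside the tested treatment.** With the nodal boost, pelvic irradiation and hormone therapy he receives most of the regimen, and the trial concerns pelvic nodal relapse.

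The conclusion rests on reading inclusion criterion 6 and non-inclusion criterion 5 together; both are poorly translated, and no sentence names the combination. The available text passes from section C to section E and cites a section 8.5.1 that it does not contain. A rule elsewhere cannot be ruled out, so confidence is medium.

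**What to change.** 1. In Management of previously irradiated patients, extend the exclusion so that it applies when any PTV1-5 or the PB relapse PTV received more than 20 Gy in an earlier course.
2. Repeat the condition in inclusion criterion 6: an associated bed relapse is allowed only if its PTV received no more than 20 Gy before.
3. Put the same condition on the PB relapse PTV line under Dose prescription.
4. State that item c) restricts only the whole-bed PB PTV, so that a relapse site with 20 Gy or less is treated under item d). Without this, items c) and d) would still conflict below the threshold.

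Saying only that item c) overrides item d) would tidy the wording but leave the lesion undosed. Referral to the quality assurance committee alone would set no limit.

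The cost is a short wording amendment. The cumulative dosimetry and the 20 Gy isodose needed to apply it are already required. The downside is that men whose bed relapse received more than 20 Gy become ineligible.

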PROTOCOL OLIGOPELVIS 1_GETUG P07

A) CLINICAL TRIAL IDENTIFICATION

STUDY TITLE	Multicentric phase II study of high-dose radiotherapy and hormone therapy in oligometastatic relapses of the pelvic lymph nodes of prostate cancer
SHORT TITLE	OLIGOPELVIS 1_GETUGP 07
INVESTIGATOR COORDINATOR	Pr [name]
ID-RCB	2014-A00138-39
REF ANSM	140494B-12 AUTORISATION 13/06/14
ETHICS COMMITTEE NAME	CPP OUEST-IV
REF ETHICS COMMITTEE	19/14 SESSION OF 13/05/14
N° CLINICAL TRIAL.GOV	NCT02274779

B) STUDY BACKGROUND

There is a growing body of evidence reporting the existence of a subset of prostate cancer patients who, at relapse, present with a limited number of metastases (fewer than five lesions). This oligometastatic state has also been identified in other tumor types, such as melanoma, soft tissue sarcoma, liver, lung, and breast cancers, and has led to a shift in management toward more aggressive local treatments, including surgical resection.

Positron Emission Tomography–Computed Tomography (PET-CT), using tracers such as choline or acetate, has proven to be a reliable tool for detecting oligometastatic disease following biochemical recurrence in prostate cancer. For patients in this setting, an intensified therapeutic approach—combining androgen deprivation therapy (ADT) with high-dose radiation therapy directed at PET-CT-detected lesions—may be proposed.

This strategy has the potential to prolong the interval between successive courses of ADT or, in selected patients with a limited metastatic burden, may even offer the possibility of cure.

In this study, the investigators aim to evaluate the 2-year biochemical or clinical relapse-free survival of prostate cancer patients with 1 to 5 oligometastases treated concomitantly with high-dose conformal radiation therapy and LH-RH agonists.

C) STUDY INFORMATION

INDICATION	Oligometastatic lymph nodes pelvic prostate cancer patients	
METHODOLOGY	Non randomized, prospective, national multicentre, phase II	
Primary Objective and Endpoint		
Primary objective	Endpoint	Evaluation time
The primary objective is to evaluate the biochemical or clinical relapse-free survival at 2 years.	The primary endpoint is the 2-year relapse-free survival probability. Biochemical or clinical relapse is defined as: 
 • A PSA level higher than the pre-treatment PSA value, confirmed by 	2 years

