It is difficult to accurately identify a control population. The recent adoption of FCH PET has enabled the detection of metastases in patients in biochemical relapse which the usual imaging modalities (bone scan, CT chest, abdomen and pelvis, pelvic MRI) were unable to detect. These patients therefore represent an intermediate group between patients with a rising PSA alone, and frank metastatic disease. To calculate the patient population, we can only rely on studies relating to a rising PSA patient population on one hand, and on first-line metastatic patients on the other hand. Prospective randomized data gathered from patients with a rising PSA showed that the median duration of biochemical control was 20 months with intermittent ADT [1]. Prospective randomized data concerning intermittent ADT in metastatic patients showed that 75 % of patients had resumed ADT after a mean duration of 15 months off [3]. Based on retrospective data, Ost et al. estimated that 51 % of patients are progression-free one to three years after salvage surgery or radiotherapy for pelvic oligometastatic disease [10]. Moreover, Rischke et al. showed a 50 % clinical recurrence at 2 year for patients undergoing both salvage lymphnode dissection and pelvic radiotherapy [18]. We therefore estimate that a biochemical relapse-free survival at 2 years of 70 % would be a significant result. Based on a one-step Fleming design [19], we wish to be 95 % ($\alpha < 5\%$) certain that any difference observed between the standard and experiment treatment groups is not due to the play of chance. We also want to be able to detect such a difference with 95 % power ($b = 5\%$). With these α and b , rejecting the null hypothesis $H_0: \Pi \leq 50\%$, and accepting the alternative hypothesis $H_1: \Pi \geq 70\%$, will require 63 evaluable patients.

	
Around 10 % of patients may be lost to follow-up before the evaluation of biochemical relapse at 2 years, so to ensure that we retain at least 63 patients until this evaluation it will be necessary to recruit 70 patients to this study. If 39 or more of these 63 evaluable patients are still free of biochemical relapse at 24 months, we may reject the null hypothesis $H_0: \pi \leq 50\%$ with a risk of error of 3.85 % and a power of 93.5 % to detect the alternative hypothesis $H_1: \pi \geq 70\%$.

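### The 70% target and the 39-of-63 success rule name biochemical relapse only, while the primary endpoint is biochemical and/or clinical relapse; the composite was very probably meant, but the rule does not say so

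*Combined protocol and SAP*

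**What the plan says.** Section B gives the aim as the composite: "the investigators aim to evaluate the 2-year biochemical or clinical relapse-free survival of prostate cancer patients with 1 to 5 oligometastases". Section C repeats it: "The primary objective is to evaluate the biochemical or clinical relapse-free survival at 2 years". The endpoint there has two limbs joined by and/or. One is a PSA above the pre-treatment value, confirmed by two consecutive increases in the same laboratory. The other is more metastatic sites on follow-up imaging.

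Sample size determination in section F uses a narrower term:

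- **Target:** "We therefore estimate that a biochemical relapse-free survival at 2 years of 70 % would be a significant result".
- **Loss allowance:** about 10% of patients "lost to follow-up before the evaluation of biochemical relapse at 2 years".
- **Success rule:** "If 39 or more of these 63 evaluable patients are still free of biochemical relapse at 24 months", the null hypothesis of at most 50% may be rejected, with a stated error of 3.85% and power of 93.5% at 70%.

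Nothing in that section links these phrases to the composite. Secondary endpoint a) is itself called biochemical relapse-free survival and uses a nadir-based threshold of 0.2 ng/mL. The paragraph on survival endpoints defines PFS by biochemical-clinical failure or death from any cause. For the failure definition it points to a section 8.5.1, which is not in the supplied text.

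**The concern.** The sentence that decides whether the null hypothesis is rejected names an event that is not the primary endpoint. The two differ for one kind of patient: one whose imaging shows more metastatic sites while the PSA does not meet the confirmed-rise criterion. That patient fails the primary endpoint but counts towards the 39 if the rule is followed as written.

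Two things would be at stake. If such patients occur, the literal rule is easier to meet than the primary endpoint. It is also not stated which event the 50% and 70% describe, so a reader cannot be sure that the quoted error and power belong to the primary endpoint.

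**Working it through.** **1. The plan's own figures.** Inputs from Sample size determination: null 50%, alternative 70%, 5% error, 95% power, 63 evaluable patients, success at 39 or more, 10% loss.

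- Normal approximation for a one-step, one-sided design: n = [(1.645·√(0.5·0.5) + 1.645·√(0.7·0.3)) / 0.2]² = 62.1, rounded up to 63.
- Exact binomial: P(X ≥ 39 | n = 63, p = 0.5) = 0.0385, the stated 3.85%.
- Exact binomial: P(X ≥ 39 | n = 63, p = 0.7) = 0.9356, the stated 93.5% apart from rounding.
- Recruitment: 63 / (1 − 0.10) = 70.

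The arithmetic is sound. The loss allowance gives 70 whichever event is named, so its wording decides nothing.

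**2. Who is counted differently.** The comparison is between the composite and a literal rule that uses the primary PSA limb alone.

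| Patient at 24 months | Primary endpoint | Literal rule |
|---|---|---|
| Qualifying PSA rise, with or without more sites | failure | failure |
| More sites, no qualifying PSA rise | failure | success |
| Neither | success | success |

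So the literal success rate equals the composite success rate plus the proportion of imaging-only failures.

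**3. Illustration: the null describes the composite, the count uses PSA alone.** Let x be the average number of imaging-only failures per 63. The documents give no value, so x is assumed. With a true composite rate of 50%, the literal rate is p = 0.5 + x/63.

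| x | p | P(X ≥ 39) |
|---|---|---|
| 0 | 0.5000 | 3.85% |
| 1 | 0.5159 | 6.5% |
| 2 | 0.5317 | 10.3% |
| 3 | 0.5476 | 15.6% |

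**4. If 50% and 70% were both meant for biochemical relapse.** The hypothesis and the count then match and the error stays at 3.85%, but the test is not of the primary endpoint. If the rule were then applied to the composite, its power would be taken at p = 0.7 − x/63:

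- x = 1: p = 0.6841, power 89.2%
- x = 2: p = 0.6683, power 83.3%
- x = 3: p = 0.6524, power 75.6%

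**5. How large x might be.** In the schedule of assessments the only imaging row is FCH PET, marked at inclusion and at progression. Under secondary endpoint e), other imaging depends on the location of recurrence and the centre's practice. With no routine imaging before progression, few failures should be found on imaging alone. At x = 0 nothing changes.

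**6. Which event the benchmarks describe.** Two lie close to the 50% null and are not purely biochemical: "51 % of patients are progression-free one to three years after salvage surgery or radiotherapy for pelvic oligometastatic disease", and a series that "showed a 50 % clinical recurrence at 2 year for patients undergoing both salvage lymphnode dissection and pelvic radiotherapy". Another is biochemical: "median duration of biochemical control was 20 months with intermittent ADT". A further one concerns resumption of ADT. The benchmarks lean away from a biochemical-only null but do not settle the matter.

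**The case against.** The strongest reply is that the primary endpoint is already fixed. The study aim, the primary objective and the endpoint definition all state the composite, and the survival analysis uses biochemical-clinical failure. The sample size text is a rationale and sets up no rival definition, so its wording is naturally read as shorthand. The missing section 8.5.1 may also define the terms. Most of this stands: it is why the composite is taken as very probably meant. It does not remove the mismatch, because the success rule appears only in this section and its words name another event.

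Three stronger readings are tempting, and the documents do not support them.

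- **The error rate is inflated.** A reader might infer that the true type I error exceeds 5%. That holds only if 50% describes the composite, the count uses PSA alone, and imaging-only failures occur. The documents establish none of these for the analysis as it would be run.
- **The rule uses secondary endpoint a).** This rests on a shared name in the target sentence. The rule does not cite that endpoint, and footnote (e) of the schedule defines biochemical progression by a criterion like the primary PSA limb, not by 0.2 ng/mL.
- **The event is open to choice after the data are seen.** The composite is pre-specified as the primary endpoint, so this is conjecture.

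**Conclusion.** The rule is wrong as written, and this should be fixed. The 70% target and the 39-of-63 criterion are worded for biochemical relapse, while the primary endpoint is biochemical and/or clinical relapse. The conclusion rests on the wording alone and needs no assumed rate.

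The size of the effect is unknown and probably small. The 6.5% to 15.6% range is conditional on the mixed reading and on assumed counts, so it shows sensitivity and is not an estimate of bias. A reader might also infer that the sample size is wrong. It is not: every stated figure reproduces and stands if 50% and 70% describe the composite. Confidence is high that the wording conflicts. The intended meaning is an inference, though a strong one.

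**What to change.** Under Sample size determination:

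1. Reword the success rule to count patients free of biochemical or clinical relapse, as defined for the primary endpoint, at 24 months.
2. Give the 70% target the same composite name and, for consistency only, do likewise in the loss sentence. Keep the name biochemical relapse-free survival for secondary endpoint a).
3. Confirm that 50% and 70% refer to the composite. If they do, 63 evaluable, 70 recruited, 39 of 63, 3.85% and 93.5% all stand. If 70% was a biochemical-only expectation, restate the power for the composite.
4. In the same edit, state whether a relapse-free death before 24 months is a failure under the rule. PFS in the survival paragraph counts death; the endpoint definition in section C does not mention it.

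**Cost:** wording only, provided the two rates are confirmed and the handling of deaths is settled. The downside is that the observed success rate may be lower by 1/63 = 1.6 percentage points for each imaging-only relapse among 63 patients.
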